About right	78%
Too much	0%
Frequency of calls at end of study (%)	
Too little	43%
About right	57%
Too much	0%
Recommend to others (%)	
Yes	96%

Fig. 7. Qualitative feedback of health coaching

based
Health that
A

Randomized Study:

Participants will be randomly assigned in equal proportion to one of two treatments: home PR with health coaching or the attention waitlist control (Fig. 9). Participants randomly assigned to the intervention will receive three months of home PR followed by six months of usual care.

Participants randomly assigned to the active control group will receive three months of usual care plus educational materials and non-coaching calls (matching the number of contacts in the intervention group), followed by three months of home PR plus health coaching and three months of usual care.

Phase 2: Participants randomized to intervention will not change; three months of home PR followed by six months of usual care. Participants enrolled in the active control group will follow the scheme listed above; 3 months of usual care followed by three months of home PR and three months of usual care. During the control wait period they will receive a pamphlet of 12 Healthy Habits during the enrollment period as well as two letters during the control period. The letters will remind them to review the 12 Healthy Habits and will remind them that the exercise portion of the study will start soon.

Phase 3: Forty Mayo participants who have completed the intervention (the 12 weeks of home-based pulmonary rehab with health coaching) will be randomly selected to complete a qualitative interview to explore areas related to the intervention, quality of life and symptom severity. The purpose of the qualitative interview is to take an in-depth look at the appropriateness of the intervention as a potential method of treatment as well as examining the impact on the participant as a whole. Mayo Clinic participants who have completed the intervention portion of the study will be contacted via the telephone to inquire about their interest in participating in the interview. If interested, oral consent will be conducted. A mutually agreed upon time and date for the interview will be confirmed. (A phone script will be used.) The participants will receive \$40 for consideration of their time.

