For the continuous study outcomes, changes from baseline to three months will be compared between the study arms using two-sample, two-sided t-tests with 5% type I error rates. Changes in QOL and number of steps will be compared between the two treatment sequences using two-sample two-sided t-tests. No adjustments will be made for multiple testing. Means, SDs, medians, ranges, and frequency distributions will be reported and plotted over time by study arm. Additional analyses will compare changes from baseline to three months. Linear models will be used to assess the impact of treatment arm on three month outcomes after adjusting for the corresponding baseline measure and other variables related to the outcome (age, degree of breathlessness at baseline using the mMRC, and FEV1). Repeated measures mixed models will be used to estimate the intervention effect over the three months of the comparison study. Although there is a crossover element to the study design, crossover analyses will not be used due to the anticipated carryover effect in the intervention arm. Intent-to-treat analyses will also be performed to determine the sensitivity of the results to dropouts and missing values. In the intent-to-treat analyses, if a month three measure is missing for any reason, it will be described as not changing from baseline. Health care utilization (number of ED visits, hospitalizations, and length of stay) between baseline and three months will be treated (analyzed) as both binary (for incidence rates) and continuous (for the number of events). The binary endpoints will all be compared between groups using Fisher's exact test. Logistic regression models will also be fit to look for differences in these outcomes by arm after adjusting for age, mMRC, FEV1, baseline levels of anxiety, depression, and fear, and baseline health care utilization (before starting the study). While significant missing-ness (>5%) in the Aim 1 outcome is not expected, imputation is planned in case it is.

Descriptive summaries of the changes between baseline, three, six, and nine months will be used to assess the effect of the delayed intervention on the control arm and the residual beneficial effect on the intervention arm. These results will be only descriptive and exploratory. No formal hypothesis testing will be done. All data will be stored in REDCap and analyzed using SAS (Cary, NC).

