Integration with Aims 1-3: The function of the mixed-methods design is elaboration of the quantitative data on effectiveness with the qualitative findings. After initial quantitative and qualitative analyses are complete, the investigators will place findings side-by-side to explore connections as well as divergent findings that need further exploration. This includes within- and between-case analysis to understand the perspectives of participants who differed on comparative effectiveness outcomes (Aim 1-3) as well as those who differed in important baseline characteristics such as participant activation.

Sample Size: We will enroll a total of 200 participants, with 100 in each arm. Sample size calculations are based on two-sample, two-sized t-tests comparing the two groups at 3 months. **Aim 1:** We calculated the sample size based on estimates from our previously published data⁶. From this research, the CRQ has a SD of about 1.13. A total sample of 189 participants (94 or 95 per group) is needed to detect a difference of 0.5 (the minimal clinically important difference) in the CRQ with 80% power. Based on our previous health coaching application (R01HL09468 [name], PI),⁶ we expect 5% attrition. We will therefore enroll 200 participants, 100 in each arm.

Aim 2: A sample size of 128 is needed to detect a half SD change in SMAS-30 based on COPD studies using this measure. **Aim 3:** The number of steps recorded by the AM is considered a valid measure of PA in patients with COPD and the elderly. The clinically meaningful difference in steps is estimated at 1100. Therefore, a sample size of 170 participants (85 per group) is needed considering a SD of 2500 steps from our previous study.⁶ **Aim 4:** The sample size of 40 completed participant interviews is within standards for qualitative research, but interviewing and analysis will take place concurrently and iteratively to inform the sampling plan. We will continue interviewing until saturation (the point at which interviews are not yielding much new information) is reached; the sample

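### Aim 1 sample size: SD 1.13 and a difference of 0.5 need 164 participants for 80% power, not 189; 189 gives about 86% power or implies an SD of about 1.22

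*Combined protocol and SAP*

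**What the plan says.** The Sample Size section describes its method as follows: "Sample size calculations are based on two-sample, two-sized t-tests comparing the two groups at 3 months". I read the word before 't-tests' as a slip for two-sided.

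For Aim 1 it says that "the CRQ has a SD of about 1.13", citing the investigators' earlier published work. It then states: "A total sample of 189 participants (94 or 95 per group) is needed to detect a difference of 0.5", naming 0.5 as the minimal clinically important difference and 80% as the power. It allows 5% attrition on top of the 189 and arrives at 200 enrolled, 100 per arm.

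The other inputs are given elsewhere in the same document:

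- **Type I error and tested quantity** (Analysis Plan): "changes from baseline to three months will be compared between the study arms using two-sample, two-sided t-tests with 5% type I error rates".
- **Multiplicity** (Analysis Plan): "No adjustments will be made for multiple testing".
- **Allocation** (Randomized Study): "Participants will be randomly assigned in equal proportion to one of two treatments".

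**The concern.** Every input that a two-sample t-test calculation needs is stated, so the sample size should follow without further assumptions. It does not: 189 is 25 more than the inputs require.

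This is the only power statement for Hypothesis 1. Aim 1 also has the largest requirement of the three quantitative aims (189, against 128 for Aim 2 and 170 for Aim 3), and the enrolment of 200 is derived from it. What the statement means depends on which entry is wrong. With the printed SD, the trial has more power than claimed and ample room for loss. With the SD that 189 implies at 80% power, there is almost no room beyond the planned 5% attrition. A reader cannot tell which case applies.

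The meaning of the SD is also open. The Sample Size section speaks of comparing groups at 3 months and does not say whether 1.13 is the SD of the 3-month score or of change from baseline, whereas the Analysis Plan tests change. This does not explain the discrepancy, but it has to be settled when the entry is corrected.

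**Working it through.** **Inputs.** Difference 0.5, SD 1.13, power 80% (Sample Size); two-sided 5% level, no multiplicity adjustment (Analysis Plan); 1:1 allocation (Randomized Study).

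**Attempt to reproduce 189.**

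Normal approximation, per group: n = 2 (z₀.₉₇₅ + z₀.₈₀)² (SD/difference)² = 2 × 7.849 × (1.13/0.5)² = 80.2, so 81 per group and 162 in total.

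Noncentral t with standardized difference 0.5/1.13 = 0.442: 81.15 per group, so **82 per group and 164 in total**.

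The stated figure is not reproduced: 189 − 164 = 25, and 189/164 = 1.15, an excess of 15%.

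**What 189 delivers** (noncentral t, 94 and 95 per group):

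- Power at SD 1.13 and difference 0.5: 85.7%.
- Difference detectable with 80% power at SD 1.13: 0.463.
- SD that gives 80% power for a difference of 0.5: 1.220. In the other direction, SD 1.22 needs 94.43 per group, 188.9 in total, which rounds up to 189.

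**Possible explanations, all other inputs as stated:**

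| Explanation | Total | Supported by the text? |
|---|---|---|
| Rounding of SD (1.125 to 1.135) | 80.44 to 81.86 per group, so 162 to 164 | Yes, but does not reach 189 |
| 5% attrition already included | 164/0.95 = 172.6, so 173 | No; attrition is applied after 189 |
| One-sided 5% test | 128 | No; two-sided stated |
| Alpha 0.025 | 198 | No; no adjustment stated |
| 1.13 is a variance | 144 | No; called an SD |
| 85% power | 186 | No; 80% stated |
| 90% power | 218 | No; 80% stated |
| Rank test, worst-case efficiency 0.864 | 164/0.864 = 189.8 | No; t-tests stated |
| Unstated 15% allowance | 164 × 1.15 = 188.6 | No; none mentioned |
| SD 1.22 | 188.9, so 189 | No; 1.13 stated |

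Several routes come close to 189, and the text supports none of them.

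**Attrition step.** 189/0.95 = 198.9, enrolled as 200. This step is correct.

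**Same method on the other aims.** No power is stated for Aims 2 and 3. At an assumed 80%, Aim 2 (half an SD) needs 128, as stated. Aim 3 (1100 steps, SD 2500) needs 166 against the stated 170, which has about 81% power. Only Aim 1 is far off.

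**Power with 200 enrolled, difference 0.5:**

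| Evaluable per group | Loss | SD 1.13 | SD 1.22 |
|---|---|---|---|
| 95 | 5% | 85.9% | 80.2% |
| 90 | 10% | 83.9% | 78.1% |
| 82 | 18% | 80.4% | 74.2% |

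**The case against.** Four points can be made for the plan.

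**The discrepancy is conservative on the printed inputs.** With SD 1.13 the trial has more power than stated, and no test, analysis set or enrolment figure changes. This stands. It limits the consequence but does not make the figures agree.

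**SD 1.22 is back-solved.** It appears nowhere as a planning input, and 85% power or an unstated allowance comes close to 189 as well. This also stands: 1.22 is one possible explanation, to be checked against the source calculation.

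**The only change SDs in the document are smaller.** Fig. 6 gives SDs of 0.9 to 1.0 for change in CRQ physical function, from the health coaching trial that carries the same citation number as the SD of 1.13. At 95 per group, SDs of 1.0 and 0.9 would give about 93% and 97% power for a difference of 0.5. That points away from an underpowered test of change. However, these values are at 6 and 12 months after coaching alone, so they are only illustrative for a 3-month home rehabilitation comparison. The pilot's CRQ domain scores in Fig. 4 have SDs from 0.6 to 1.5, so a score SD near 1.2 is not excluded.

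**The narrow margin assumes 200 enrolled.** The Target accrual paragraph gives 400, with site targets of 150 + 70 + 70 = 290. At SD 1.22, 145 per group would give about 94% power. This is a fair condition on the adverse case. But the Sample Size section rests its power claim on 200, and the conflict between the two targets is a separate point.

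**Conclusion.** The concern holds. The stated SD, difference, power, test and allocation need 164 evaluable participants, and the stated 189 exceeds this by 15%. At 189, power is 85.7% rather than 80%, or the SD used was about 1.22 rather than 1.13. Rounding, attrition and multiplicity are ruled out by the document's own text.

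This is an error of reporting or calculation. It does not show that the trial is too small: if 1.13 is the right SD for the tested quantity, Aim 1 has about 86% power after 5% loss. The result assumes a two-sided 5% test, equal groups and the enrolment of 200 in the Sample Size section. Which entry is wrong cannot be decided from the documents.

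**What to change.** Check the source calculation and correct the entry that is wrong:

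- **If 189 at 80% power is right:** state the SD actually used (about 1.22), and note that the 5% attrition allowance is then essentially the whole margin, with about 78% power at 10% loss.
- **If SD 1.13 is right:** replace the sentence with wording such as: *164 evaluable participants (82 per group) give 80% power; 200 enrolled with 5% attrition (95 per group) give about 86%.* Only in this case may the text add that 80% power survives about 18% loss.
- **If a higher target power or an extra allowance was used:** state it.

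In every case, say whether the SD is for the 3-month score or for change from baseline, and match it to the t-test on change in the Analysis Plan.

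The cost is a text correction. The enrolment of 200 in the Sample Size section does not change.

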“Very helpful. Very visual. Tablet was portable which allows people who need visual training to follow along.”
“Wasn’t that difficult, could see where if someone would stick with it they would benefit.”

Were there things you didn’t like?

“I mentioned to the day that you showed me this that the slow walking bothered to me, but then when you explained to me that the slow walking really helps me work on my balance, I really thought about it and plan to really work on it.”

Is there anything we could do differently or that we need to change?

“I think the human component is very important, to feel that someone is checking up. It would be nice to have variation in the exercises. I don’t think I could do the same exercises for 8 weeks. I really liked the pursed lipped breathing exercise.”

Fig. 8. Qualitative pilot feedback of the home pulmonary rehabilitation program.

Study Design and Methods

Methods: *Describe, in detail, the research activities that will be conducted under this protocol:*

Pilot Study: When the technology is ready, we will conduct a pilot study enrolling fifteen or fewer participants. The participants in the pilot study will not be randomized and will receive the Intervention. The purpose of the pilot study is to observe how the technology works in real life and to refine the intervention if needed. The participants in the pilot study will complete all measures and activities of the randomized control trial, minus the randomization.

Characteristic	Control	Intervention	NNT	P Value
CRQ Emotional Function				
Δ6 Month – Baseline, mean (SD)	0.10 (1.0)	0.50 (1.0)		0.004
Δ12 Month – Baseline, mean (SD)	0.15 (0.9)	0.43 (1.0)		0.058
% improved >MCID at 6 months	14.1	29.9	6	0.018
% improved >MCID at 12 months	14.3	28.8	6	0.036
CRQ Physical Function				
Δ6 Month – Baseline, mean (SD)	-0.01 (1.0)	0.33 (0.9)		0.036
Δ12 Month – Baseline, mean (SD)	-0.04 (1.0)	0.27 (1.0)		0.016
% improved >MCID at 6 months	12.8	26.0	7	0.038
% improved >MCID at 12 months	11.4	19.2		0.199
ΔPhysical Activity Level at month 6	0.01	0.01		NS
ΔPhysical Activity Level at month 12	0.01	-0.10		NS
Died in First 12 Months, n (%)	12 (11.3%)	10 (9.3%)		0.620

NNT, Number Needed to Treat ; MCID, Minimal Clinically Important Difference

Fig. 6. Quality of life outcomes from health coaching

Qualitative Interviews	N=24
Confidence in taking care of health (mean ± SD)	8.05 ± 1.99
Helpfulness of the intervention (mean ± SD)	9.60 ± 0.60
Frequency of calls (%)	
Too little	22%

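### The 5% attrition allowance is credited to the earlier coaching trial, but that trial's month-6 results as printed imply about 28% without a CRQ change; 80% power is not assured and a month-3 loss rate needs its own justification.

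*Combined protocol and SAP*

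**What the plan says.** The Sample Size paragraph of the Analysis Plan sizes Aim 1 on a two-group comparison at 3 months. It states that "the CRQ has a SD of about 1.13", gives 189 participants (94 or 95 per group) as the number "needed to detect a difference of 0.5 (the minimal clinically important difference") "in the CRQ with 80% power", names the earlier health coaching trial as the basis for its loss rate, and concludes: "we expect 5% attrition. We will therefore enroll 200 participants, 100 in each arm".

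The Analysis Plan compares changes from baseline to three months by "two-sample, two-sided t-tests with 5% type I error rates". On missing data it says: "While significant missing-ness (>5%) in the Aim 1 outcome is not expected, imputation is planned in case it is".

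The Preliminary Data section (Project 2) gives the earlier trial's size as 215. Fig. 6 prints its results without denominators: for each CRQ domain a row "improved >MCID at 6 months", the same at 12 months, and a row "Died in First 12 Months, n" with counts and percentages by arm.

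The Target accrual section gives 400 in total, with listed site targets of 150, 70 and 70.

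**The concern.** The 5% carries the step from 189 evaluable to 200 enrolled, and the same threshold appears in the statement about missing Aim 1 data. If its named source shows a much higher loss, the evaluable count has no support in the document and the margin for the power statement is unknown.

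The loss rate also affects how the results read. The leading t-test on change uses those with a month-3 value. The intent-to-treat sensitivity analysis counts a missing month-3 value as no change. With equal loss in both arms, and the same true effect in those lost, a difference of 0.5 would shrink in that analysis to 0.5 × 0.95 = 0.475 at 5% loss and 0.5 × 0.72 = 0.36 at 28%.

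**Working it through.** **1. The plan's own figures.** Inputs from the Analysis Plan: difference 0.5, SD 1.13, two-sided 5%, power 80%, equal arms.

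- n per arm = 2 × (1.960 + 0.842)² × (1.13 / 0.5)² = 2 × 7.85 × 5.11 ≈ 80.2, so 81. The exact t calculation gives 81.15, so 82 per arm and 164 in total.
- The stated 189 is not reproduced. It corresponds to about 86% power at SD 1.13, or to an SD of about 1.22 at 80% power.
- The attrition step is reproduced: 189 / 0.95 = 199, rounded to 200. The slack is 1 − 189/200 = 5.5%.

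**2. How many the earlier trial evaluated at month 6.** Fig. 6 gives CRQ emotional 14.1% against 29.9% (P 0.018) and CRQ physical 12.8% against 26.0% (P 0.038).

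- Control: the only denominator up to the arm size that yields both percentages is 78 (11/78 = 14.1%, 10/78 = 12.8%).
- Intervention: the only one is 77 (23/77 = 29.9%, 20/77 = 26.0%).
- An uncorrected chi-square on these counts returns P 0.018 and 0.038, as printed. The same test on the death row (12/106 against 10/108) returns the printed 0.620, which supports the choice of test.
- This does not hinge on the two domains sharing a denominator. For the physical row alone, 78 and 77 is the only pair within the arm sizes that matches both percentages and the P value. The emotional row alone would also admit 85 and 67, a total of 152, which is hardly different.
- 78 + 77 = 155, and (215 − 155) / 215 = 60/215 = 27.9% without a month-6 change. This includes deaths before month 6.

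**3. Month 12 as a cross-check.** Of the denominators that fit the percentages, only 70 and 73 return the printed P values 0.036 and 0.199. That is 143 of 215, so 33.5% without data. Deaths by month 12 were 12 + 10 = 22 of 215, about 10%.

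**4. Power with 200 enrolled** (exact two-sample t, difference 0.5):

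| Loss | Per arm | Power, SD 1.13 |
|---|---|---|
| 5% | 95 | 86% |
| 10% | 90 | 84% |
| 14% (assumed: half the month-6 figure) | 86 | 82% |
| 18% | 82 | 80% |
| 28% (month-6 figure) | 72 | 75% |

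At 72 per arm with an SD of 1.0, power is 85%.

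**5. The other enrolment figures.** 150 + 70 + 70 = 290, against 400 and 200. At 27.9% loss, 290 leaves about 209 evaluable (power 89% at SD 1.13) and 400 leaves about 288 (96%).

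**The case against.** The strongest reply is that month-6 loss in another trial says little about month-3 loss here. The earlier trial aimed to reduce COPD readmission and lost about 10% to death within a year. This one excludes candidates in acute exacerbation, requires a confidence rating of at least six, and uses a waitlist design chosen for retention. That stands: 28% cannot be carried over as an estimate, and 14% is only an assumption. It does not rescue the 5%, because the plan itself names that trial as the source and shows nothing from it near 5%.

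Second, the power has slack. Because 189 exceeds what the stated inputs need, 80% survives loss of up to about 18%. The primary test is on change, and Fig. 6 shows change SDs of 0.9 to 1.0 for CRQ physical at month 6, which would keep power above 80% even at 28% loss. This also stands, with one reservation: the slack comes from an unexplained mismatch. If the 189 reflects a larger SD (about 1.22), power would be about 76% at 14% loss and 69% at 28%.

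Third, the plan already provides for imputation, mixed models, tests of the missingness mechanism and an intent-to-treat sensitivity analysis. True; and it does not say that the 5% attrition is why imputation is conditional, so a reader should not infer that link. The point is narrower: the statement that more than 5% is not expected has no support in the data shown.

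**Conclusion.** The 5% is not supported by its cited source as the document presents it: about 28% of that trial's participants had no month-6 CRQ change. The evaluable count of 189 is missed at any loss above 5.5%.

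A reader might infer that the trial is underpowered. The documents do not support that. At SD 1.13 and 200 enrolled, power falls below 80% only beyond about 18% loss, and the shortfall at 28% is about 5 percentage points. With an SD of 1.0, or with 290 or 400 enrolled, there is none. Nor do the documents show a month-3 loss of 14% to 28%; they give no month-3 retention at all. The supportable statement is that 80% power is not assured.

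This rests on the percentages and P values in Fig. 6 being printed correctly, on uncorrected chi-square tests, and on 215 as the randomised total. It warrants correction, but not a change of design.

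**What to change.** No change in enrolment is needed for this point.

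- Replace the 5% with a justified month-3 loss rate, for example the earlier trial's early retention. Failing that, state evaluable N and power over a range labelled as assumed: 5% to 28% loss, 95 to 72 per arm, power 86% to 75% at SD 1.13. Do not present any part of that range as a month-3 result from Fig. 6.
- Delete the Analysis Plan statement that more than 5% missing Aim 1 data is not expected, and set out the missing-data handling as planned rather than contingent.
- Correct the 189: either state about 164 for SD 1.13, difference 0.5 and 80% power, or give the SD or power that the 189 was based on.
- Reconcile the 200 in the Sample Size paragraph with the 400, and the site targets totalling 290, under Target accrual.

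The cost is a text edit to the sample-size, missing-data and accrual paragraphs, plus retrieving a retention figure that the investigators should already hold. At the upper end of the loss range the stated power becomes less favourable.
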